13.3. Volunteer Population

Sixty (60) volunteers. Volunteers that do not complete the study may be replaced at the discretion of the principal investigator. Volunteers will be recruited from the healthy population in the Baltimore community and the metropolitan Baltimore/Washington area.

13.3.1. Population analyzed

13.3.1.1. Definitions of Populations

Included patients: volunteers performing at least V0 (screening) visit.

Randomized patients: volunteers assigned a randomization number

Injected patients: volunteers administered at least one dose of product

13.3.1.2. Full Analysis Set

As the sample size was small, immunogenicity data will be analyzed on the population of injected volunteers in an "intent to treat" analysis. This population will be identified as the Full analysis set.

Volunteers' data will be analyzed in the treatment group allocated by randomization.

No per protocol analysis will be performed.

A complete description of protocol violations will be performed in order to investigate the possible impact of protocol violations on the immunogenicity evaluation.

Volunteers included and not injected (i.e., not in the full analysis set) will not be taken into account.

13.3.1.3. Safety Analysis Sets

The safety data will be analyzed for all volunteers who receive at least one injection (= Full analysis set). Only safety information collected after at least one injection will be taken into account. Adverse events which occur between V0 and the first injection will be listed.

In case of randomization error, a volunteer will be analyzed according to the treatment he/she actually received.

For safety evaluation "after any injection" all the volunteers injected and evaluated at least once will be considered as assessable. In case of withdrawal, it may lead to an underestimation of the occurrence rate.

Exploratory analyses will be performed (e.g., examination of frequency distributions, modality of distributions, kurtosis and skewness, etc.) for all variables collected before subjecting the values to statistical analysis.

13.3.1.4. Immunogenicity Analysis Sets

The immunogenicity data will be analyzed for all volunteers who receive at least one injection (= Full analysis set). Only safety information collected after at least one injection will be taken into account.

In case of randomization error, a volunteer will be analyzed according to the treatment he/she actually received.

Exploratory analyses will be performed (e.g., examination of frequency distributions, modality of distributions, kurtosis and skewness, etc.) for all variables collected before subjecting the values to statistical analysis.

13.4. Primary Criterion Analysis

The primary reactogenicity (safety) endpoints are occurrence of severe systemic and severe local reactions.

Separate assessments of systemic and local reactions will be performed. Each safety parameter assessed will be compared between vaccine recipients and placebo recipients as determined by Fisher exact test with a Type I error of no greater than 5%.

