2. SYNOPSIS

Name of Sponsor/Company: Sponsor: Institute of Human Virology Manufacturer: Profectus Biosciences	
Name of Investigational Product: IHV01	
Name of Active Ingredient: Full Length Single Chain (FLSC), Aluminum Phosphate	
Title of Study: A Phase I Safety and Immunogenicity Trial of IHV01, in HIV-1 Uninfected Volunteers	
Study center(s): Institute of Human Virology	
Principal Investigator: [name], M.D. Investigators: [name]. [name].	
Studied period (years): 1 year Estimated date first patient enrolled: November 2015 Estimated date last patient completed: May 2018	Phase of development: I
Objectives: Primary: To evaluate the safety and tolerability of intramuscular administration of the IHV01 at three different doses. Secondary: To evaluate the immunogenicity of three different doses of the IHV01, a full length single chain (FLSC) gp120-CD4 complex vaccine. This will be assessed by the following parameters: 1) anti-FLSC antibodies, and 2) anti gp-120 (BaL), and 3) competitive titers to CD4i epitopes.	
Methodology: Single center, randomized, dose escalation, placebo-controlled, double-blind trial	
Number of patients (planned): 60	
Diagnosis and main criteria for inclusion: Inclusion/Exclusion Criteria as in Section 7.1 and Section 7.2 .	
Investigational product, dosage and mode of administration: IHV01 in sequential dose escalation of 75 ug, 150 ug and 300 ug administered intramuscularly.	
Duration of treatment:	

Volunteers will be immunized with candidate vaccine or placebo on Days 0, 28(week 4), 56(week 8), and 168(week 24). Volunteers will continue to undergo active protocol follow up visits on Days 182(week 26), 196(week 28), 252(week 36), 294 (week 42) and 336 (week 48). The total trial time expected per volunteer is 48 weeks. The protocol recruitment period is expected to be approximately 36 weeks. The total trial duration is estimated to be approximately 72-96 weeks.

Reference therapy, dosage and mode of administration:

Placebo consisting of preservative free normal saline in volumes equal to the investigational product administered intramuscularly.

Criteria for evaluation:

Safety:

1. Monitoring and assessment of hematological, chemical, and immunologic parameters (See [Section 11.1.5](#), [Section 12.1](#), and [Table 4](#)).
2. Monitoring participants for local and systemic adverse reactions after each injection and for 12 months after the first injection ([Section 11.2](#)).
 - a. Local reactogenicity signs and symptoms

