4.5.2. Potential Risks

In theory, it is possible that immunization with gp120-CD4 complexes could induce auto-anti-CD4 responses. These could be antibody responses, T cell responses, or both. It is well established in the older immunological literature that it is possible to break tolerance to self-antigens by adding T helper epitopes. In principle, gp120 T helper epitopes could collaborate with auto-anti-CD4 B cells or CTL precursors to break tolerance to CD4 epitopes. In this regard, it is interesting to note that immunization of a chimp with soluble human CD4 elicited an antibody response against an epitope that is not present on cell surface CD4 although the sera were able to block infection of chimpanzee or human lymphocytes with HIV-1 (Watanabe, Boyson et al. 1992). Similar results were obtained in rhesus macaques immunized with human CD4 (Watanabe, Chen et al. 1991; Watanabe, Levine et al. 1991). These studies used soluble human CD4 that differs in the extracellular domain from chimp CD4 by 4 residues and macaque CD4 by 37 residues raising the question of whether tolerance was actually broken in these studies and whether it would be broken if macaques were deliberately immunized with human CD4. Deliberate immunization of cynomolgus macaques with human CD4 showed that the antibody response was selectively directed against human epitopes (Truneh, Frescatore et al. 1990). We were able to verify this result

in our immunotoxicology study using FLSC ([Study Number VTR-0018](#)). There was no evidence in this study that immunization of cynomolgus macaques with a homologous CD4 contained in rhFLSC broke tolerance. While these findings strongly indicate that the CD4 moiety of FLSC will be poorly immunogenic in humans, the risk of inducing auto-anti-CD4 antibodies drives the design of the phase 1 safety studies.

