11.1. Safety Parameters

The safety parameters to be utilized in this study are listed below. The schedule for their assessment is listed in [Table 4](#) and [Section 6.1.1](#).

1. Local and systemic vaccine reactogenicity.
2. Laboratory Safety Evaluation
3. Medical History and Physical Examination

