11.1.5. Laboratory Assessments

All abnormal laboratory values will be scored utilizing the ACTG toxicity grading system (see [Appendix 2](#)) where applicable or other appropriate criteria. Hematology and clinical laboratory evaluations will be performed by the

UMMS clinical laboratory facility. The following safety tests will be performed as outlined in the Schedule of Assessments ([Table 4](#)).

- Hematology: CBC, including differential, platelets
- Clinical Chemistries: serum electrolytes, liver function tests, renal function tests, PT/PTT
- Urinalysis: routine and microscopic, pregnancy test on women
- CD4 + T cell count
- HIV viral load by Roche-Amplicor ultra-sensitive RNA PCR

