11.1.5.6. Assessment of Vaccine Reactogenicity

The safety evaluation will include an evaluation of both local and systemic reactions to the candidate immunotherapeutic vaccines. Assessment of local reactogenicity will include erythema, induration, swelling, itching, pain and tenderness, skin discoloration, skin breakdown, and presence of subcutaneous nodules at the site of injection. Assessment of systemic reactions will include assessment of fever, chills, nausea, vomiting, arthralgia, myalgia, malaise, urticaria, wheezing, dizziness, headache. Each volunteer will complete a self-administered questionnaire/diary daily for 7 days after each immunization to assess reactogenicity. In addition, follow up telephone contact or clinic visit will be conducted by research nurse 24 to 48 hours following each immunization to record reactogenicity/adverse events. The study personnel will also conduct a careful assessment of possible adverse experiences at each clinic visit (See [Table 4](#)). Both the volunteer diary and the elicited adverse experiences will be used to determine the occurrence of adverse events. Any discrepancies between these sources will be resolved by careful review of the data with the volunteer. All adverse events will be recorded in the CRFs as noted in [Section 11.4](#).

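### Section 13.4 names no laboratory or CD4 result as a primary safety endpoint, and Section 13 defines no CD4 event to analyse, although the CD4 risk drives the design

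*Combined protocol and SAP*

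**What the plan says.** The primary objective (5.2) is safety and tolerability at three doses. The Synopsis evaluates safety in two parts: "Monitoring and assessment of hematological, chemical, and immunologic parameters", and "Monitoring participants for local and systemic adverse reactions after each injection and for 12 months after the first injection". The second part has sub-items for local reactogenicity, systemic reactogenicity, and adverse and serious adverse experiences. Section 11.1 lists "Laboratory Safety Evaluation" beside reactogenicity and history and examination, and 11.1.5 includes "CD4 + T cell count" among the safety tests. Section 4.5.2 explains why CD4 matters: "the risk of inducing auto-anti-CD4 antibodies drives the design of the phase 1 safety studies".

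The primary criterion in 13.4 is narrower: "The primary reactogenicity (safety) endpoints are occurrence of severe systemic and severe local reactions". The section then adds a general sentence, "Each safety parameter assessed will be compared between vaccine recipients and placebo recipients as determined by Fisher exact test", at a Type I error of at most 5%. Section 13.2 repeats the comparison of each safety parameter with Student's t and chi-square tests.

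On timing, 11.1.5.6 says "Each volunteer will complete a self-administered questionnaire/diary daily for 7 days after each immunization to assess reactogenicity". Section 13.4 gives no window.

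**The concern.** The primary endpoints of a first-in-human safety trial should be able to register the hazard the trial was built around. A severe local or systemic reaction, as the protocol lists them, is a symptom or an injection-site finding. A confirmed CD4 fall is neither. Nor is a low platelet count, although 4.4.2 singles out a possible platelet reduction in rabbits as the toxicology finding of most concern.

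The named primary result for a dose could therefore be clean while several volunteers had lost CD4 cells. Dose selection rests partly on the safety profile (4.2, 12.2.5). If the CD4 event is not defined beforehand, the threshold, the confirmation rule and the handling of explained declines would all be chosen once the data can be seen.

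**Working it through.** **1. Can a CD4 or laboratory result count as a named primary event?**

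| Place | Content | CD4 or laboratory item? |
|---|---|---|
| 13.4, named primary endpoints | severe systemic and severe local reactions | no |
| 11.1.5.6, reaction lists | symptoms and injection-site signs | no |
| Appendix 1, diary card | symptoms and injection-site signs | no |
| Appendix 2, grading table | laboratory rows, including platelets | no CD4 row |
| 6.4.1 and 7.3.3, halt rules | CD4 decline over 30%, confirmed at least 4 weeks apart, with a similar fall in CD4%, unexplained | yes, but as a monitoring trigger |
| 13.2 and 13.4, general sentences | each safety parameter is compared | by implication, with no event defined |

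The only CD4 event definition is in the halt rules, and Section 13 does not adopt it for analysis.

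**2. The plan's own figures.** Section 13.1 gives detectable SAE rates of 73.5% (15 v 5) and 36.8% (45 v 15) at 80% power. The continuity-corrected two-proportion formula (two-sided 0.05, control rate 0.1%, 3:1) gives 73.4% and 36.75%, so both reproduce. They concern SAEs, which are neither the severe reactions of 13.4 nor CD4 decline. The sample-size section therefore supplies no CD4 endpoint either.

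**3. What can happen under the text.** Inputs: 15 vaccine and 5 placebo volunteers per group (13.1). The halt applies at more than 5 volunteers (6.4.1) or at 5 or more (7.3.3). Suppose four vaccinees have a confirmed decline, no placebo recipient does, and nobody has a severe reaction.

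- Halt: 4 < 5 and 4 < 6, so neither version is triggered.
- Named primary endpoints: 0/15.
- CD4 rate: 4/15 = 26.7%. The Clopper-Pearson limits are the 2.5% point of Beta(4, 12) = 7.8% and the 97.5% point of Beta(5, 11) = 55.1%.
- Fisher, 4/15 v 0/5: with 4 events among 20, the probability that all fall on vaccine is C(15,4)/C(20,4) = 1365/4845 = 0.282. The two-sided p adds the tables that are no more likely: (1365 + 1050 + 150 + 5)/4845 = 2570/4845 = 0.53.
- Against pooled placebo, 4/15 v 0/15: p = 0.10.

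**4. Is a count of one to four unusual?** For an assumed true decline rate among vaccinees, P(1 to 4 of 15) = P(at least 1) − P(at least 5):

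- 10%: 0.794 − 0.013 = 0.78
- 20%: 0.965 − 0.164 = 0.80
- 30%: 0.995 − 0.485 = 0.51

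These rates are assumptions. Across them, a count below both halt thresholds but above zero is the more likely outcome.

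**5. Would a formal CD4 test help?** With no placebo events, two-sided significance at 0.05 needs 9/15 v 0/5 (p = 0.038; 8/15 gives 0.055), or 12/45 v 0/15 pooled (p = 0.027; 11/45 gives 0.051). Even 5/15 v 0/5, which meets the 7.3.3 halt, gives p = 0.27. The useful output is a rate with an interval: 0/15 has an exact two-sided 95% upper limit of 1 − 0.025^(1/15) = 21.8%.

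**6. Reaction window.** Section 11.1.5.6 and the Appendix 1 note say 7 days. The instruction printed on the Appendix 1 card asks for symptoms within 48 hours. Section 13.4 is silent.

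**The case against.** The strongest reply is that CD4 is already covered. The second sentence of 13.4, under the primary heading, applies Fisher's test to every safety parameter; 11.1 makes laboratory evaluation a safety parameter; and 11.1.5 lists CD4. Section 13.2 adds chi-square as well as the t-test, and treats each volunteer as their own control for toxicity. An unfavourable laboratory result is an adverse event under 11.2.1.1, platelets are graded in Appendix 2, and the DSMB reviews adverse events and laboratory tests at each escalation and about every three months (11.6).

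Most of this stands. A reader might infer from the first sentence of 13.4 that a CD4 fall cannot affect the primary result, counts for nothing, or survives only in a comparison of means. The documents do not support that. What the reply does not supply is a CD4 endpoint with primary status, or the binary event that its own Fisher test requires. The halt rules do not fill the gap, because they set no reporting rule for one to four cases.

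Two further inferences should be resisted. One is that the reaction rate would differ many-fold between a 7-day and a 12-month window. The Synopsis item also covers adverse events, so its 12 months reads naturally as applying to them, and any multiple would rest on background rates the documents do not give. The other is that low power of a t-test on CD4 measures this defect. That power reflects the sample size and an assumed spread, and naming an endpoint would not change it.

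**Conclusion.** The point holds as a gap in endpoint definition. Section 13.4 names only severe reactions, and Section 13 defines no CD4 event, although the protocol says the CD4 risk drives the design. The named primary endpoints can read 0/15 in a dose group where 4/15 (26.7%, 95% CI 7.8–55.1%) have a confirmed decline and no halt is triggered.

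That example assumes no severe reactions in the group and no placebo declines; it illustrates what the text allows and does not forecast a result. The textual gap depends on no assumed rate. The consequence lies in what is prespecified and reported as primary safety. It does not show that CD4 loss would go unseen during the trial, and adding a test would gain little at this size.

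**What to change.** In 13.4, add two per-volunteer primary safety endpoints:

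1. Confirmed CD4 decline, using the definition common to 6.4.1 and 7.3.3 (over 30%, confirmed at least 4 weeks apart, with a similar CD4% decline). State whether the judgment that a decline is unexplained applies, ideally reporting with and without it, and how the two baseline counts in 6.1.1.1 are combined.
2. Any Grade 3 or higher laboratory value after the first injection.

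Report each by dose group and for pooled placebo with an exact 95% CI, descriptively.

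State that solicited reactions are counted over the 7 diary days after each injection (11.1.5.6), and that the Synopsis 12-month period applies to adverse events. Reconcile the 48 hours and the 7 days in Appendix 1. The different CD4 halt counts in 6.4.1 and 7.3.3 must also be reconciled, as a separate matter.

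The cost is amendment wording, a corrected diary card and more primary safety summaries. No new visit, sample or assay is needed.

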13.5. Secondary Criterion Analysis

Immunogenicity parameters will be compared using response and non-response as well as mean medium and geometric mean of titers between vaccine recipients and placebo recipients as determined by Wilcoxon matched pairs test or the Sign test and the Fisher exact test. Immunogenicity parameters will be compared between dose groups of the FLSC vaccine as well as between each to placebo recipients. Exploratory analyses will be performed (e.g., examination of frequency distributions, modality of distributions, kurtosis and skewness, etc.) for all variables collected before subjecting the values to statistical analysis.

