4.2. Trial Design Overview

This study is designed to evaluate the safety of the IHV01 vaccine and will be a randomized, placebo-controlled, modified double-blinded dose escalation study in 60 healthy adult volunteers. Although there is a great deal of experience with protein vaccines, the optimal dose of IHV01 given intramuscularly is not known. Therefore, this trial is designed as a dose escalation trial in order to determine the optimal dose to move forward with in future clinical trials. This dose will be chosen after reviewing the safety and immunogenicity data from this trial. Alum has been chosen as an adjuvant due to the extensive amount of safety data available. The study will have 3 arms including placebo, 75 µg dose, 150 µg dose, and 300 µg dose and will last for 336 days (48 weeks). Volunteers will be immunized on Day 0, Day 28(4 weeks), Day 56(8 weeks), and Day 168(24 weeks). Each dose group will have 15 vaccine and 5 placebo recipients. The dosage schedule in this trial was based on the animal data and data with other envelope protein vaccines, and is patterned after the schedule utilized in the RV144 trial in Thailand. From this trial, an optimal dose of the candidate vaccine will be chosen for use in future trials. It is anticipated that the trial will be enrolled and completed 18 months after it is open to enrollment.

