8.4. Randomization and Blinding

Volunteers will be randomized using block randomization in a 3:1 ratio of FLSC:placebo. They will be block randomized in groups of 4 with each study group. This will be done by the research pharmacist utilizing random # generator called Stat Trek. There will be 5 groups of 4 volunteers in each randomized block (each block will have 3 FLSC recipients and 1 placebo recipient).

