12.1. Endpoint Evaluations of Immunogenicity

12.1.1. Immunogenicity Endpoint

The primary evaluation of immunogenicity will consist of the generation of antibodies to FLSC as determined by antibody titration using FLSC as the detection antigen. A positive vaccine response will be defined as a 4-fold increase in antibody directed against native FLSC protein by ELISA. In addition geometric mean antibodies titers will be assessed and compared among groups.

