12.2. Immunogenicity Assays

12.2.1. Endpoint Assay

ELISA based assay using FLSC protein will be used. A positive vaccine response will be defined as a 4-fold increase in antibody directed against native FLSC protein by ELISA.

The human serum samples collected before and after immunization will be analyzed, after a 1 hour heating step at 60°C, for the presence of anti-FLSC_I antibodies (total IgG) by the ELISA technique. To determine whether the development of anti-FLSC antibodies is really linked to a specific immune stimulation following vaccination and not to a general immune activation, all sera will be also tested against an irrelevant HIV antigen, p24, that is not cross-reactive with FLSC. In this case, the titers against p24 should remain constant. The results will be expressed as half-maximal antibody titers in arbitrary units (log).

The ELISA assays will be conducted as follows: 6 to 12 serial three-fold dilutions of the serum samples, starting at 1/10, will be tested in 96-well ELISA plates pre-coated with the antigen of interest (*ie* FLSC or p24). The presence of specific antibodies will be revealed by addition of an anti-human total IgG peroxidase-conjugate, followed of a chromogenic hydrogen peroxide-specific substrate. Finally, each well will be read by an automatic plate reader at an optical density (OD) of 450-650 nm.

The background will be given by the blanks (*ie* 6 to 12 wells with all the reagents except sera) which OD values should not exceed 0.2 in average. The OD values from all samples will be subtracted from this mean blank OD. One negative control, a serum from an HIV-negative volunteer, will be present on each ELISA plate. Its OD value, subtracted from the mean blank OD, should not exceed 0.2 at the lowest dilution (1/100).

Two anti-FLSC (or anti-p24) human sera will be on on each ELISA plate: one, with a predetermined antibody titer (see below*), will serve as the standard: *ie* all sample titers will be calculated from the regression curve of this standard ($OD = f(\text{inverse dilution})$) using the SoftMaxPro software (Molecular Devices). The second positive serum will be used as the positive control: its mean titer (m) and the corresponding standard deviation (sd), will have to be calculated from the standard after several independent experiments. The assay will be considered as valid if the titer of this positive control measured on the ELISA plate is included in the titer range: $m \pm 3 \text{ sd}$ (log).

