12.2.5. Data Analysis

Immunogenicity parameters will be compared using response and non-response as well as mean medium and geometric mean titers between vaccine recipients and placebo recipients (i.e. Arms 1 and 2 compared to Arm 3) as determined by Student's T test *and chi-square analyses*. Immunogenicity parameters will be compared between FLSC in Arms 1, 2, and 3 as well as between the placebo recipients (Arms 1 to 3 and 2 to 3). Exploratory analyses will be performed (e.g., examination of frequency distributions, modality of distributions, kurtosis and skewness, etc.) for all variables collected before subjecting the values to statistical analysis. Cross-sectional parametric and non-parametric analyses will be conducted on variables exhibiting normal and non-normal distributions, respectively, to examine differences and trends among treatment categories.

The dose selected will be that which provides the optimal CD4i epitope immunogenicity and antiviral activity and safety profile. Based on our results in macaques, we believe that the FLSC will be safe even when administered at the highest dose of 300 µg. Titers will be evaluated for normality (Kolmogorov-Smirnov test) then compared via a parametric test such as one-way analysis of variance (ANOVA). If the data fails the normality test we will use the Kruskal-Wallis test (3-group comparison) and Wilcoxon rank-sum test (2-group comparison) to compare groups. A p value < 0.05 will indicate that one of the vaccination regimens elicits significantly higher response in that measure versus the others.

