13.2. Statistical Methods

Each safety parameter assessed will be compared between vaccine recipients and placebo recipients as determined by Student's T test *and chi-square analyses*. In addition safety parameters will be compared between vaccine dose groups as well as to placebo recipients. In addition each volunteer will serve as their own control for the occurrence of toxicity. Adverse reaction as defined in Appendix 1 and 3 will be reported independent of a statistical association.

Immunogenicity parameters will be compared using response and non-response as well as mean medium and geometric mean titers between vaccine recipients and placebo recipients as determined by Student's T test *and chi-square analyses*. Immunogenicity parameters will be compared between vaccine dose groups as well as between each to placebo recipients. Exploratory analyses will be performed (e.g., examination of frequency distributions, modality of distributions, kurtosis and skewness, etc.) for all variables collected before subjecting the values to statistical analysis. Cross-sectional parametric and non-parametric analyses will be conducted on variables exhibiting normal and non-normal distributions, respectively, to examine differences and trends among treatment categories.

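### Section 13.5 compares titers in separate vaccine and placebo recipients with paired tests, defines no pairs, and conflicts with 12.2.5 and 13.2

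*Combined protocol and SAP*

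**What the plan says.** Section 13.5 (Secondary Criterion Analysis) compares titers "between vaccine recipients and placebo recipients as determined by Wilcoxon matched pairs test or the Sign test", and adds Fisher's exact test. It also asks for comparisons between dose groups and of each dose group with placebo.

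The design gives two independent groups. Section 4.2 states: "Each dose group will have 15 vaccine and 5 placebo recipients". Section 8.4 randomises 3:1 in blocks of four, where "each block will have 3 FLSC recipients and 1 placebo recipient". Section 13.1 gives the pooled numbers as 45 and 15.

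Other sections name different tests for the same contrast:

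- Section 13.2: "Immunogenicity parameters will be compared using response and non-response as well as mean medium and geometric mean titers between vaccine recipients and placebo recipients", by Student's t test and chi-square. It continues: "Cross-sectional parametric and non-parametric analyses will be conducted on variables exhibiting normal and non-normal distributions, respectively".
- Section 12.2.5 repeats the t test and chi-square. In a later paragraph, mainly about choosing between doses, it adds: "If the data fails the normality test we will use the Kruskal-Wallis test (3-group comparison) and Wilcoxon rank-sum test (2-group comparison) to compare groups".

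The outcome is a log titer. Section 12.2.1 says "The results will be expressed as half-maximal antibody titers in arbitrary units (log"), and section 12.1.1 says "In addition geometric mean antibodies titers will be assessed and compared among groups".

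**The concern.** The matched-pairs Wilcoxon and the Sign test work on one difference per pair. With 15 and 5 unrelated volunteers there are no such differences unless someone invents a pairing. The result would then depend on that invention, and most of the vaccine recipients in a dose group could be left out.

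Section 13.5 is the section specific to the immunogenicity criterion, so it would normally be followed over the general text in 13.2. A literal reader therefore reaches the test that cannot be used. A practical reader must choose among the tests named elsewhere. Section 13.9 controls deviations from the statistical plan, but choosing a test that the plan already names is arguably not a deviation.

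Two related wording conflicts sit in the same sections:

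- **Safety tests.** The general safety comparison ends with t test and chi-square in 13.2 and the synopsis. In 13.4 it ends with Fisher's exact test at no more than 5%, which is also the test that 13.1 assumes.
- **Significance level.** Section 13.6 calls the significance level not pertinent, yet 12.2.5, 13.1 and 13.4 all use 0.05.

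**Working it through.** **The plan's own figures.** The plan gives no power or sample size for immunogenicity. Its only power figures, in 13.1, are detectable SAE rates of 73.5% (15 v 5) and 36.8% (45 v 15). A two-sided continuity-corrected formula with a 0.1% control rate returns 73.4% and 36.75%. Those figures concern safety and do not bear on this point.

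**Is there a pairing rule?** No. The only grouping of volunteers is the randomisation block (8.4), which holds three vaccine recipients and one placebo recipient and is not one-to-one. The only statement that a volunteer acts as their own control (13.2) concerns toxicity. Section 13.5 names the contrast as vaccine against placebo, not before against after.

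**Smallest attainable two-sided p-value**

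| Analysis | Formula | Smallest p |
|---|---|---|
| Sign or signed-rank, 5 pairs (one dose group) | 2 × 0.5^5 | 0.0625 |
| Sign or signed-rank, 15 pairs (all placebo recipients) | 2 × 0.5^15 | 0.00006 |
| Exact rank-sum, 15 v 5 | 2 / C(20,5) = 2 / 15,504 | 0.00013 |
| Fisher on response, 15/15 v 0/5 | 1 / C(20,5) = 1 / 15,504 | 0.00006 |

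Five pairs leave 15 − 5 = 10 vaccine recipients unused in a dose group. Fifteen pairs leave 45 − 15 = 30 unused if the whole vaccine group is compared.

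**Arbitrariness.** Choosing one of three vaccine recipients in each of five blocks gives 3^5 = 243 possible pairings per dose group. Setting each placebo recipient against the block's vaccine mean removes the choice, but keeps five differences and the 0.0625 floor.

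**Power within one dose group (15 v 5), two-sided 0.05.** Simulation with 4,000 runs per shift. Assumptions: normal log titers, equal SD, illustrative shifts that are not from the plan.

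| Shift (SD) | Exact rank-sum | t test | Signed-rank on 5 block differences |
|---|---|---|---|
| 1.0 | 40% | 46% | 0% |
| 1.5 | 72% | 78% | 0% |
| 2.0 | 92% | 95% | 0% |

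The last column follows directly from the 0.0625 floor.

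**Safety tests (secondary).** Pooled 45 v 15, no placebo events:

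| Vaccine events | Chi-square, uncorrected | Chi-square, corrected | Fisher |
|---|---|---|---|
| 9 | 0.060 | 0.144 | 0.095 |
| 10 | 0.0455 | 0.110 | 0.0535 |
| 11 | 0.034 | 0.083 | 0.0505 |
| 12 | 0.025 | 0.062 | 0.027 |
| 13 | 0.019 | 0.047 | 0.026 |

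The tests disagree at 0.05 only for 10, 11 and 12 of 45 (22% to 27%). Enumerating the exact size over common event rates, uncorrected chi-square peaks at 5.2% (15 v 5, rate 50%) and 5.5% (45 v 15, rate 21%), just above the 5% limit in 13.4. At a common rate of 10% its size is 2.2% and 3.5%. Fisher's maximum is 2.5% and 3.5%.

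**The case against.** The strongest reply is that the 0.0625 floor depends on a choice the plan does not make. Section 13.5 does not say that each dose group is compared only with its own five placebo recipients. If all 15 are used, 15 pairs can reach 0.00006. That stands: the floor applies only to pairing within a dose group. It does not rescue the sentence, because those 15 pairs are equally undefined.

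Second, no section sets 0.05 for this contrast. Section 13.5 gives no level, 13.6 disclaims one, and the threshold in 12.2.5 is worded for comparing vaccination regimens. This is fair, and it is a further reason to align 13.6. The floor is a defect only if 0.05 is used as a benchmark.

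Third, the conflict with 12.2.5 and 13.2 is partly inferred. Neither calls its t test unpaired, although for 15 v 5 separate people it can only be the two-sample form. The rank-sum sentence is mainly about dose. Section 12.2.5 also describes vaccine against placebo as Arms 1 and 2 against Arm 3, but Group 3 in Table 3 is the 300 µg group with its own placebo recipients. That is another error to correct, not a defence.

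Fourth, the consequences are limited. This is a secondary objective, the Fisher test on response is valid, and section 8.4.2 breaks the codes only after database lock. For safety, 13.4 is the specific section and would ordinarily govern. Without a continuity correction, which the plan never mentions, chi-square and Fisher differ only at 10 and 11 of 45. The excess of chi-square over 5% is at most about half a percentage point. All of this limits the severity, but none of it says which titer test applies.

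**Conclusion.** The concern holds. Section 13.5 names tests that do not fit the design, and it disagrees with 12.2.5 and 13.2 on the same comparison. This is an error in a stated rule, not a missing detail.

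Its size depends on how pairs might be invented. One-to-one within a dose group, significance at two-sided 0.05 is impossible. With all 15 placebo recipients it is possible but arbitrary. The power comparison rests on assumed normal log titers with equal SD and illustrative shifts; the p-value floors need no such assumption.

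The error should be corrected before analysis. It affects the reported immunogenicity comparisons, not dose escalation, stopping or the responder analysis. The safety and significance-level conflicts are real but minor.

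**What to change.** - **13.5:** replace the paired tests with the exact Wilcoxon rank-sum test for vaccine against placebo titers. Keep Fisher's exact test for response. If change from before to after immunization is wanted, say so, and use the signed-rank or Sign test only there.
- **12.2.5 and 13.2:** replace chi-square with Fisher's exact test for response, to match 13.5. The t test may stay for log titers, because it compares the geometric means that the plan reports, provided one test is named in advance as the main one. Correct the arm labels in 12.2.5, and state whether each dose group is compared with its own 5 or with all 15 placebo recipients.
- **13.2 and synopsis, safety:** for binary outcomes, name Fisher's exact test at 5%, as in 13.1 and 13.4. The t test may stay for continuous laboratory values.
- **13.6:** align with the 5% level used in 12.2.5, 13.1 and 13.4.

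The cost is statistical wording in those sections. Sample size, visits and assays do not change.
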